11.3 Response Criteria

Secondary outcomes will be measured using the response assessment for Neuro-oncology (RANO) criteria⁵⁸ applied to follow-up medical imaging. Specifically, complete response, partial response, stable disease or progressive disease will be determined using volumetric measurements of brain tumor enhancement and clinical measures of neurological decline.

1. Complete response requires all of the following: complete disappearance of all enhancing measurable and nonmeasurable disease sustained for at least 4 weeks; no new lesions; stable or improved nonenhancing (T2/FLAIR) lesions; patients must be off corticosteroids (or on physiologic replacement doses only); and stable or improved clinically. Note: Patients with nonmeasurable disease only cannot have a complete response; the best response possible is stable disease.
2. Partial response requires all of the following: > 50% decrease compared with baseline in the sum of products of perpendicular diameters of all measurable enhancing lesions sustained for at least 4 weeks; no progression of nonmeasurable disease; no new lesions; stable or improved nonenhancing (T2/FLAIR) lesions on same or lower dose of corticosteroids compared with baseline scan; the corticosteroid dose at the time of the scan evaluation should be no greater than the dose at time of baseline scan; and stable or improved clinically. Note: Patients with nonmeasurable disease only cannot have a partial response; the best response possible is stable disease.
3. Stable disease will require all of the following: does not qualify for complete response, partial response, or progression; stable nonenhancing (T2/FLAIR) lesions on same or lower dose of corticosteroids compared with baseline scan. In the event that the corticosteroid dose was increased for new symptoms and signs without confirmation of disease progression on neuroimaging, and subsequent follow-up imaging shows that this increase in corticosteroids was required because of disease progression, the last scan considered to show stable disease will be the scan obtained when the corticosteroid dose was equivalent to the baseline dose.
4. Progression will be defined by any of the following: > 25% increase in sum of the products of perpendicular diameters of enhancing lesions compared with the smallest tumor measurement obtained either at baseline (if no decrease) or best response, on stable or increasing doses of corticosteroids; significant increase in T2/FLAIR nonenhancing lesion on stable or increasing doses of corticosteroids compared with baseline scan or best response after initiation of therapy not caused by comorbid events (e.g., radiation therapy, demyelination, ischemic injury, infection, seizures, postoperative changes, or other treatment effects); any new lesion; clear clinical deterioration not attributable to other causes apart from the tumor (e.g., seizures, medication adverse effects, complications of therapy, cerebrovascular events, infection, and so on) or changes in corticosteroid dose; failure to return for evaluation as a result of death or deteriorating condition; or clear progression of nonmeasurable disease.

These criteria are published and currently accepted in the neuro-oncology community⁵⁸. The imaging interpretation will be completed by a board certified neuro-radiologist, while the neurological outcome/status will be assessed by a board certified neurologist/neuro-oncologist.

PDT Phase II Trial – Glioma Tumors In Adults

12.0 ADVERSE EVENT REPORTING REQUIREMENTS

12.1 Purpose

Adverse event (AE) data collection and reporting, which are required as part of every clinical trial, are done to ensure the safety of patients enrolled in the studies as well as those who will enroll in future studies using similar agents. Certain adverse events must be reported in an expedited manner to allow for timelier monitoring of patient safety and care. The following sections provide information about expedited reporting.

12.2 Expedited Reporting Requirements

See Next Page...

12.2.1 Adverse Events that Occur on Studies under an IND/IDE within 30 Days of the Last Administration of the Investigational Agent/Intervention¹

FDA REPORTING REQUIREMENTS FOR SERIOUS ADVERSE EVENTS (21 CFR Part 312)

NOTE: Investigators **MUST** immediately report to the sponsor **ANY** Serious Adverse Events, whether or not they are considered related to the investigational agent(s)/intervention (21 CFR 312.64)

An adverse event is considered serious if it results in **ANY** of the following outcomes:

- 1) Death
- 2) A life-threatening adverse event
- 3) An adverse event that results in inpatient hospitalization or prolongation of existing hospitalization for ≥ 24 hours
- 4) A persistent or significant incapacity or substantial disruption of the ability to conduct normal life functions
- 5) A congenital anomaly/birth defect.
- 6) Important Medical Events (IME) that may not result in death, be life threatening, or require hospitalization may be considered serious when, based upon medical judgment, they may jeopardize the patient or subject and may require medical or surgical intervention to prevent one of the outcomes listed in this definition. (FDA, 21 CFR 312.32; ICH E2A and ICH E6).

ALL SERIOUS adverse events that meet the above criteria **MUST** be immediately reported to the Sponsor-Investigator within the timeframes detailed in the table below.

Hospitalization	Grade 1 and Grade 2 Timeframes	Grade 3-5 Timeframes
Resulting in Hospitalization ≥ 24 hrs.	10 Calendar Days	Initial Report: 24-Hours Full Report: 5 Calendar Days
Not resulting in Hospitalization ≥ 24 hrs.	Not required	

Expedited AE reporting timelines are defined as:

- “24-Hour; 5 Calendar Days” - The AE must initially be reported within 24 hours of learning of the AE, followed by a complete expedited report within 5 calendar days of the initial 24-hour report.
- “10 Calendar Days” - A complete expedited report on the AE must be submitted within 10 calendar days of learning of the AE.

¹Serious adverse events that occur more than 30 days after the last administration of investigational agent/intervention and have an attribution of possible, probable, or definite require reporting as follows:

Expedited 24-hour notification followed by complete report within 5 calendar days for:

- All Grade 3, 4, and Grade 5 AEs

NOTE: Investigators **MUST** immediately report to the sponsor **ANY** Serious Adverse Events, whether or not they are considered related to the investigational agent(s)/intervention if they occur within 90 days after the last administration of investigational agent/intervention.

Expedited 10 calendar day reports for:

- Grade 2 AEs resulting in hospitalization or prolongation of hospitalization

12.3 Expedited Reporting the Sponsor Investigator Examples

12.3.1 SAEs Occurring More than 30 Days After Last Dose of Study Drug

Any Serious Adverse Events (SAEs) occurring *within 30 days* of the last dose, regardless of attribution to the investigational agent/intervention requires expedited reporting within 24 hours. Any SAE occurring *greater than 30 and up to 90 days* after the last dose of the investigational agent/intervention requires expedited reporting within 24 hours **only if** it is possibly, probably, or definitely related to the investigational agent/intervention.

12.3.2 Persistent or Significant Disabilities/Incapacities

Any AE that results in persistent or significant incapacity or substantial disruption of the ability to conduct normal life functions (formerly referred to as disabilities), congenital anomalies or birth defects, must be reported to the sponsor if it occurs at any time following treatment with an agent under an IND/IDE since these are considered serious AEs.

12.3.3 Death

Any death occurring *within 30 days* of the last dose, regardless of attribution to the investigational agent/intervention requires expedited reporting within 24 hours. Any death occurring *greater than 30 and up to 90 days* after the last dose of the investigational agent/intervention requires expedited reporting within 24 hours **only if** it is possibly, probably, or definitely related to the investigational agent/intervention.

Reportable Categories of Death

- Death attributable to a CTCAE term
- Death Neonatal: A disorder characterized by cessation of life during the first 28 days of life.
- Sudden Death NOS: A sudden (defined as instant or within one hour of the onset of symptoms) or an unobserved cessation of life that cannot be attributed to a CTCAE term associated with Grade 5
- Death NOS : A cessation of life that cannot be attributed to a CTCAE term associated with grade 5
- Death due to progressive disease should be reported as ***Grade 5 “Neoplasms benign, malignant and unspecified (includes cysts and polyps) - Other (Progressive Disease)*** under the system organ class (SOC) of the same name. Evidence that the death was a manifestation of underlying disease (e.g., radiological changes suggesting tumor growth or progression: clinical deterioration associated with a disease process) should be submitted.

12.4 Reporting Methods for SAEs

Steps to Determine if an Adverse Event Related to DRUG or the Regimen as a Whole is to be Reported in an Expedited Manner

Step 1: Identify the event type using the NCI Common Toxicity Criteria (CTC), version 4.0.

The CTC provides descriptive terminology and a grading scale for each adverse event listed. A copy of the CTC can be downloaded from the CTEP home page (<http://ctep.cancer.gov>). Additionally, if assistance is needed, the NCI has an Index to the CTC that provides help for classifying and locating terms. All appropriate treatment locations should have access to a copy of the CTC.

Step 2: Grade the event using the NCI CTCAE.

This study will utilize version 4.0 of the CTCAE of the National Cancer Institute (NCI) for toxicity and performance reporting. A copy of the CTCAE version 4.0 can be downloaded from the CTEP website. Additionally, toxicities are to be reported on the appropriate case report forms.

Step 3: Determine whether the adverse event is related to the protocol therapy.

The investigator will assess the causal relationship between the investigational product and the adverse event. The investigator will use his/her clinical expertise and judgment to select the attribution category below that best fits the circumstances of the AE.

Attribution Categories:

❖Unrelated❖	❖Unlikely❖	❖Possible❖	❖Probable❖	❖Definite❖
-------------	------------	------------	------------	------------

Unrelated:

- The adverse event is clearly unrelated to the investigational agent(s).
- Does not follow a known response pattern to the suspect investigational product (if response pattern is previously known)
- Can be explained by the known characteristics of the patient's clinical state or therapy administered to the patient

Unlikely:

- a. The adverse event is doubtfully related to the investigational agent(s).
- b. May or may not follow a reasonable temporal sequence from administration of the investigational product.
- c. Likely explained by the known characteristics of the patient's clinical state

or other therapy administered to the patient

Possibly Related:

- a. The adverse event may be related to the investigational agent(s).
- b. Follows a reasonable temporal sequence from administration of the investigational product
- c. May also be reasonably explained by the patient's clinical state or therapy administered to the patient.
- d. May follow a known response pattern to the investigational product (if response pattern is previously known)

Probably Related:

- a. The adverse event is likely related to the investigational agent(s).
- b. Follows a reasonable temporal sequence from administration of the investigational product
- c. May follow a known response pattern to the investigational product (if response pattern is previously known)
- d. Could not be reasonably explained by the known characteristics of the patient's clinical state or other modes of therapy administered to the patient, if applicable;

Definitely Related:

- a. The adverse event is clearly related to the investigational agent(s).
- b. Follows the temporal sequence from administration of the investigational product
- c. Follows a known response pattern to the investigational product
- d. Cannot be explained by the known characteristics of the patient's clinical state or other therapy administered to the patient
- e. Is confirmed by improvement of symptoms on stopping or slowing administration of the investigational product and re-emergence of symptoms on restarting administration of the investigational product, (if applicable)

Step 4: Determine the prior experience of the adverse event.

Expected events are those that have been previously identified as resulting from administration of the agent. An adverse event is considered unexpected, for expedited reporting purposes only, when either the type of event or the severity of the event is not listed in the toxicities listed in the drug information section of the protocol.

Step 5: Report the adverse events as outlined in the protocol.

12.5 Reporting Requirements – Investigator Responsibilities

Clinical investigators in the treating institutions and ultimately the Study Chair have the primary responsibility for AE identification, documentation, grading, and assignment of attribution to the investigational agent/intervention. It is the responsibility of the treating physician to supply the medical documentation needed to support the expedited AE reports in a timely manner.

Note: All expedited AEs must also be reported via routine reporting. Routine reporting is accomplished via the Adverse Event (AE) Case Report Form (CRF) within the study database.

12.6.1 Additional Protocol Specific Reporting Requirements

12.6.1 Reporting to the Medical College of Wisconsin/Froedtert Hospital IRB

The Principal Investigator will submit timely reports to the MCW/FH IRB including any unanticipated problems, serious adverse device and drug events occurring during the investigation, and any deviation from the investigational plan, either unintentional or made to protect the life or physical wellbeing of a subject in an emergency. Any UPIRSO's, Internal Adverse Events, Adverse Device or Drug Effects, or other events meeting the MCW/FH IRB prompt reporting criteria will be reported no later than 5 calendar days after the study team becomes aware of the problem, event or information. All other adverse events will be reported at time of continuing review in accordance with MCW/FH IRB policy. Non-serious Adverse Events (collected from Day 0 to Day +30/1-Month follow-up) and non-serious/administrative protocol deviations will be collected and reported on an annual basis as per MCW/FH IRB policy. SAEs (collected from Day 0 to Day +90) that are unrelated to the study will be reported to the IRB on an annual basis via the DSMC Study progress reports. Refer to section 13.3 for details. SAEs require DSMC expedited review will be reported to the IRB within 5 calendar days.

12.6.2 Reporting to Pinnacle Biologics, Inc.

The industry collaborator, Pinnacle Biologics, Inc. is an international company with obligations in several European countries to quickly report all SAEs from all ongoing clinical trials using Photofrin®. We have developed a reporting plan that will facilitate Pinnacle's reporting requirements while safeguarding patient's confidentiality.

Reporting Serious AEs:

The investigator will report each SAE, regardless of causality, within 24 hours of awareness by

e-mail, or fax to the Pinnacle Biologics, Inc. third party Drug Safety delegate. This includes SAEs occurring as soon as the patient or patient's legally representative signs the informed consent (i.e., pre-treatment SAEs). The SAE form provided by Pinnacle Biologics, Inc. should be completed as thoroughly as possible, given the information available and time constraints. A full initial report accompanied by additional relevant information documenting the occurrence of the event should be forwarded to the Drug Safety delegate within 4 calendar days (in case of death or life-threatening events) or 7 calendar days (for other SAEs) respectively. Follow up report should be forwarded within the next 5 calendar days (in case of death or life-threatening events) or as soon as this information is available (for other type of events).

In addition, any spontaneously reported SAE that occurs within 30 days after the last study procedure for patient who completed the study protocol or within 90 days after the Photofrin® injection for patients who prematurely discontinued study treatment should be recorded and reported.

Other Events Requiring Expedited Reporting:

The following events should be also reported to the Drug Safety delegate within 24 hours of awareness:

- Any pregnancy that occurs to study patients. Drug exposure during pregnancy should be reported on the "Pregnancy Exposure form" provided by Pinnacle Biologics, Inc.
- Drug or light dose overdose with or without adverse events
- Inadvertent or accidental exposure to the study drug with or without adverse events
- All other medication errors (use of expired medication, dosing errors, etc.) with or without adverse events
- Suspected transmission of an infectious agent
- SAEs that meet the criteria for expedited reporting to the Data Safety Monitoring Committee for this clinical trial. Refer to section 13.3.

Reporting Non-Serious AEs

Non-serious Adverse Events should be collected by the Investigator, but do not require expedited report to Pinnacle Biologics, Inc. Because this protocol is a FDA IND study, these events are to be reported periodically (as per FDA regulations) by Pinnacle Biologics, Inc. and listed in the final study report. Listings will be provided to Pinnacle Biologics, Inc. periodically.

12.6.3 Reporting to the Data Safety Monitoring Committee

Please refer to section 13.3.

12.7 Routine Adverse Event Reporting

Routine reporting is accomplished via the Adverse Event (AE) Case Report Form (CRF) within the study database. For this study, routine reporting will include all expedited reportable events and Grade 3 and higher Adverse Events.

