11.0 EVALUATION CRITERIA

11.1 Common Terminology Criteria for Adverse Events (CTCAE)

This study will utilize version 4.0 of the CTCAE of the National Cancer Institute (NCI) for toxicity and performance reporting. A copy of the CTCAE version 4.0 can be downloaded from the CTEP website. Additionally, toxicities are to be reported on the appropriate case report forms. Refer to sections 12 and 13 for details.

Please note: 'CTCAE v4.0' is understood to represent the most current version of CTCAE v4.0 as referenced on the CTEP website (ie, v4.02 and all subsequent iterations prior to version 5.0).

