APPENDIX 1: PHOTODYNAMIC THERAPY (PDT) EVALUATION TABLE

STANDARD OF CARE & STUDY SPECIFIC EVENTS & EVALUATIONS	PRE-STUDY	TREATMENT PHASE			POST-OP FOLLOW-UP				LONG-TERM FOLLOW-UP		
	Day -30 To Day 0	Day 0: Photofrin®	Day +1: PDT Photoillumination	Day +2 To Discharge: Post-Op Care	Week 1 To 4 (Week No.): 1 2 3 4				Week 5 to 13: (Patient SOC Plan)	Week 24: (6 Months Post PDT)	Week 52 to 156: (Patient SOC Plan)
SCREENING											
Neuro-Oncology Eligibility Review	X	X									
ENROLLMENT & REGISTRATION											
Informed Consent	X ²		X								
HIPAA Authorizations for Follow-Up Reports	X ²										
Eligibility Checklist & Registration CRFs	X ²										
TREATMENT											
Photofrin® Dose Calculation, Preparation, & Duration (Start & Stop Time)		X ²									
Tumor Resection			X								
PDT Photoillumination Dose Calculation, Preparation, & Duration (Start & Stop Time)			X ²								
ACUTE POST-OP CARE											
Dexamethasone Dose			X ¹	X ¹	X ¹	X ¹	X ¹	X ¹			
Intracranial Pressure Monitoring			X ¹	X ¹							
LABS											
CBC	X			X ¹	X ¹	X ²	X ¹	X ¹			
BUN	X ²			X ¹	X ¹	X ²	X ¹	X ¹	X ¹		
Creatinine	X ²			X ¹	X ¹	X ²	X ¹	X ¹	X ¹		
ALT	X ²			X ¹	X ¹	X ²	X ¹	X ¹	X ¹		
AST	X ²			X ¹	X ¹	X ²	X ¹	X ¹	X ¹		
Total Bili	X ²			X ¹	X ¹	X ²	X ¹	X ¹	X ¹		
ALK	X ²			X ¹	X ¹	X ²	X ¹	X ¹	X ¹		
PT	X ²			X ¹	X ¹	X ²	X ¹	X ¹	X ¹		
PTT	X ²			X ¹	X ¹	X ²	X ¹	X ¹	X ¹		
Other ¹	X ¹			X ¹	X ¹	X ¹	X ¹	X ¹	X ¹		
EVALUATIONS											
H & P	X		X	X	X	X	X	X	X	X	X
Skin Exam	X	X	X	X	X	X	X	X	X ¹		
Karnofsky Score	X			X	X	X	X	X	X ¹	X	X ¹
Neurologic Exam	X		X	X	X	X	X	X	X ¹	X	X ¹
MRI Brain	X			X	X ¹	X ¹	X	X	X ¹	X	X ¹
MRI Total Spine	X ¹			X ¹	X ¹	X ¹	X ¹	X ¹	X ¹	X ¹	X ¹
Required CTCAE Reporting [Grade(s)]	1-5	1-5	1-5	1-5	1-5	1-5	1-5	1-5	3-5		
All Concomitant Medications	X	X	X	X	X	X	X	X	X ¹		
Anti-Cancer Therapy: Chemo/XRT/Surgery									X	X	X
Disease Evaluations									X ¹	X	X ¹
Survival Status/Cause of Death (if applicable)	X	X	X	X	X	X	X	X	X	X	X

X Required Reporting & SOC for the Patient

X¹ Recorded IFF Clinically Indicated According to the Patient's SOC

X² Required Study Event; Not SOC

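### Sections 12.7, 12.6.1 and Appendix 1 disagree on which adverse events are recorded, and non-serious Grade 1-2 photosensitivity is not scheduled for recording after about Day 30

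*Combined protocol and SAP*

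**What the plan says.** Four places govern what is recorded.

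- Section 12.5 names the channel: "Routine reporting is accomplished via the Adverse Event (AE) Case Report Form (CRF) within the study database". Section 12.7 repeats it and gives the scope: "routine reporting will include all expedited reportable events and Grade 3 and higher Adverse Events". It sets no end date. Section 11.1 leads the reader there: "toxicities are to be reported on the appropriate case report forms. Refer to sections 12 and 13 for details".
- Appendix 1, in the row that begins "Required CTCAE Reporting [Grade(s", asks for Grades 1-5 in every column from pre-study to Week 4, Grades 3-5 in Weeks 5-13, and nothing later.
- Section 12.6.1, on reporting to the IRB, gives two windows and no grade floor: "Non-serious Adverse Events (collected from Day 0 to Day +30/1-Month follow-up" and "SAEs (collected from Day 0 to Day +90".
- Section 12.6.2, on reporting to the industry collaborator, has the investigator collect non-serious events, with no grade limit and no window, for listing in the final report.

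The expedited table in 12.2 asks for no report of Grades 1 and 2 in the row "Not resulting in Hospitalization ≥ 24 hrs". After 30 days, if at least possibly related, "Grade 2 AEs resulting in hospitalization or prolongation of hospitalization" remain reportable.

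On the reaction itself, 6.3.1 says that sensitivity can persist to 90 days or beyond in some patients, 6.3.2 continues eye precautions until the sensitivity has gone, and 6.4 describes the reactions as mainly mild or moderate.

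**The concern.** A coordinator who follows 12.7 to the letter would enter Grade 3 and higher events and expedited events, and could leave a first-month mild sunburn-type reaction off the form. One who follows Appendix 1 would enter it. After Day 30 the conflict moves to non-serious Grade 3 events, which Appendix 1 requires and 12.6.1 places outside its window.

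The second issue is the window. The photosensitivity that the protocol describes is mainly low grade and can outlast the first month, and low grades are what drop out of scheduled recording at about Day 30.

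At stake is secondary objective 1.2.1, a descriptive account of safety and tolerability, and the table of adverse events by frequency and severity that 13.3.1 requires for the DSMC. Uneven recording would make those tables hard to interpret. A Day 30 figure read as covering the whole photosensitive period could understate both incidence and duration.

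**Working it through.** The plan gives no figure to reproduce, so the check sets the passages side by side.

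| Event | 12.7 | 12.6.1 | Appendix 1 |
|---|---|---|---|
| Non-serious Grade 1-2, through Week 4 | not listed | collected | required |
| Non-serious Grade 3 or higher, Days 31-90 | listed | outside window | required |
| Non-serious Grade 1-2, Days 31-90 | not listed | outside window | not required |
| Serious, Days 31-90 | Grade 3 or higher, or expedited | collected | Grades 3-5 required |

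Rows 1 and 2 are direct disagreements. Row 3 is the gap. Section 12.6.2 does not clearly close it: it asks for non-serious events without saying for how long, while the two places that do set a window both stop. Row 4 shows no gap up to Day 90.

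**Windows.** Week 4 ends at 4 × 7 = Day 28 and Week 13 at 13 × 7 = Day 91. Scheduled Grade 1-2 recording therefore stops at Day 28 (Appendix 1) or Day 30 (12.6.1). Up to Day 90 that leaves 90 − 30 = 60 days. This is calendar time. It is not a share of risk or of events.

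**Does the protocol treat 90 days as relevant?** Yes, in several places. Section 5.1.3 gives 30 to 90 days for light precautions. Section 5.3 asks for 90 days of toxicity evaluation in patients who do not receive the full drug dose or complete the light treatment. Under 6.3.3, patients test a small skin area in sunlight before resuming exposure, and 6.3.1 has them avoid direct sun for at least 30 days first. That re-exposure can therefore fall after Grade 1-2 recording has stopped.

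**Scale.** The documents give two anchors.

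- Section 6.4 gives about 20% in cancer patients: 0.20 × 30 = 6.0 patients here. The exact 95% interval for 6/30 is 7.7% to 38.6%.
- The team's earlier 20-patient brain tumour study, described just before 2.6.5, reports no skin or eye photosensitivity. The exact 95% upper limit for 0/20 is 1 − 0.025^(1/20) = 16.8%. Doses there were lower: 0.75 to 2.0 mg/kg in Appendix 4, against 2.5 mg/kg here.

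Neither anchor gives onset time or grade distribution. As pure assumption, if 0%, 10% or 50% of the 6.0 reacted only after Day 30 and at low grade, then 0, 0.6 or 3.0 patients would be missed, and the recorded rate would be 6.0/30 = 20%, 5.4/30 = 18% or 3.0/30 = 10%. With the earlier study as anchor, the loss could be zero throughout.

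**The case against.** The strongest reply is that 12.7 says what routine reporting includes and does not say that nothing else is recorded. Read as a minimum, it does not contradict Appendix 1. Several passages support that reading. Section 13.2 has the forms completed from the patient's calendar. Section 8.1 makes Appendix 1 the table of evaluations needed for the aims and for safety monitoring. Section 12.6.2 wants non-serious events in the final report, and the DSMC table in 13.3.1 has no Grade 3 floor. This stands in large part. A reader might infer that first-month mild reactions will be missing from the safety report; that would need staff to follow one sentence and disregard all of these. What remains is that no passage says 12.7 is a minimum, and the minimum reading does not resolve the Day +30 limit in 12.6.1.

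On the window, the reply is that Appendix 1 tiers collection deliberately, with all grades in the acute month and the more severe grades afterwards. That is a legitimate choice, and a result labelled as running to Day 30 would be accurate. Section 6.3.3 also says that ambient light gradually inactivates the residual drug, so risk should fall over time. Some late events may surface anyway, because Appendix 1 requires a history and physical in Weeks 5-13 and 5.1.3 tells patients to contact their physician about a reaction. These points make the window a modest matter. They do not change the fact that mild late reactions need not be entered.

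A reader might also infer that adverse event collection as a whole ends before the photosensitive period. It does not, up to about Day 90, for Grades 3-5 or serious events.

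**Conclusion.** The disagreement between 12.7, 12.6.1 and Appendix 1 is in the text and should be removed. Appendix 1 is the better-supported reading, but the documents do not settle the point. The lack of scheduled recording for non-serious Grade 1-2 skin and eye reactions after about Day 30 is real and narrow.

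The size is unknown. The scenarios above rest on assumed shares, and a loss of 0.6 patients would be small against an interval of 7.7% to 38.6%. The 69% rate that 6.4 gives for Barrett's esophagus is from a different population and is not used here. The primary endpoint and the Grade 4 or higher skin and eye triggers in 13.3.2 are unaffected, and 10.4 treats the secondary objectives as exploratory. This is a minor improvement, worth making because it is cheap.

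**What to change.** 1. Align 12.7 and 12.6.1 with Appendix 1, so that Grades 1-5 through Week 4 and all Grade 3 and higher events in Weeks 5-13 go on the adverse event form. This is a text correction.
2. For skin photosensitivity and ocular sensitivity only, record Grades 1-5 to Day +90, the window that 12.6.1 already uses for serious events. Take them from the Weeks 5-13 history and physical and from patient reports, with a resolution date. No visit is added.
3. Report descriptively the proportion with a reaction by Day 30 and by Day 90. Show how many died or were lost before Day 90, since eligibility asks only for a life expectancy above 8 weeks (8 × 7 = 56 days). State that ascertainment after Week 4 depends on standard-of-care visits.

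The cost is slight extra recording for two terms. Late ascertainment may be incomplete, because 5.1.7 sets no study-specific time points after the first month and Appendix 1 has the Weeks 5-13 skin exam recorded only when clinically indicated. Attribution becomes harder once other anticancer therapy starts, which 5.2.2 allows from about one month. Section 5.2.2 already has that therapy's schedule recorded, so its start date can be shown beside late reactions.
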